- Patients with inability to take medication orally due to swallowing problems in which it is not indicated to place a nasogastric tube.
- Pregnant or breastfeeding patients.
- Patients in a GCS 3 points situation with bilateral dilated pupils.
- Patients with associated spinal cord injuries.
- Patient with any systemic condition that contraindicates the use of corticosteroids.

Randomization

To ensure a balanced sample size across groups over time, the statistician of the study will apply the block randomisation method with a block size of 2 (two possible sequences: AB and BA) and will be generated with the statistical package R, version 3.5.3, a list for each hospital. A limited number of treatments will be available in each

hospital, sent from the Pharmacy Department of Son Espases Hospital, which will be numbered, and will be assigned in a correlative manner.

Patients, clinical staff, evaluators of the results as well as the statistical team will be blinded to the assignment of medications.

Only the pharmacist, who masks the capsules and labels the containers, will know the assignment of the codes, and will keep them blind until the last phase of the study, after the main statistical analysis, or when unmasking is required.

Once it is verified that the patient meets all the inclusion criteria and none of the exclusion criteria, and after signing the informed consent by the patient himself or by the closest relative, the doctor responsible for the patient will correlative assign the number to the patient.

Settings

Initially, the study will be carried out in Son Espases Hospital (Palma de Mallorca) and 12 de Octubre Hospital (Madrid). During the first year, all possible patients will be tried to be recruited. A minimum of 60 patients are expected between the two hospitals.

If after the first year interim analysis the Trial Steering Committee (TSC) decides to continue the trial, recruitment will begin in the hospitals included in the Spanish National Registry of Traumatic patients in the ICU (RETRAUCI Network) which includes 56 public hospitals.

Outcome measures

After a patient has been randomized, the outcome will be collected even if the trial treatment is interrupted or is not actually given

Primary outcome

The primary outcome is the functional status (outcome) of TBI patients one and six months after the trauma according to the Glasgow Scale Outcome Extended (GOSE).

Secondary outcomes (Supplemental data)

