-Number of episodes of neurological deterioration in both groups of patients during the 12 days of treatment.

- Symptoms associated with TBI in both groups of patients during the 12 days of treatment.
- Volume of pericontusional edema before and after 12 days of treatment in both groups of patients.
- Presence of adverse events between the two groups during the 12 days of treatment.
- Neuropsychological tests between the two groups of patients one month and 6 months after the TBI.

Estimated event rate

In our previous studies we have described that among TBI patients with brain contusions not treated with dexamethasone, the proportion of patients with good recovery (GOSE 7 and 8) was 50%.

Sample size and treatment effect size that should be detectable

Since the data available in this type of patients with this treatment is scarce and inconclusive, we will perform a randomized, triple-blind, placebo controlled trial with an interim futility analysis (interim analysis). The primary endpoint for the DEXCON TBI trial is the good recovery (GOSE 7-8) one month after the TBI.

A study with 600 patients would have about 80% power (two sided alpha=5%) to detect a 12% absolute increased (from 50% to 62%) in good recovery (GOSE 7-8). It includes an inflation of 10% due to non-adherence (withdrawal of consent, loss to follow-up, cross-over or change of treatment).

Recruitment of collaborating investigators

The trial will recruit hospitals from Spain. Suitable collaborating hospitals and investigators will be assessed in terms of the trauma service that they provide and their ability to conduct the trial.

Before the trial can begin at any site, the local Principal Investigator must agree to adhere to Good Clinical Practice Guidelines and all relevant national regulations. In addition, all relevant regulatory and ethics approvals should be in place before the trial starts at a site.

Ethical considerations, information giving and written informed consent

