The primary analysis will compare all patients allocated to dexamethasone versus those allocated to placebo, on an 'modified intention-to-treat' basis. Modified intention-to-treat basis, which will include all patients who were randomly assigned, except those who withdrew consent, those who were lost the follow up or had protocol violations. Protocol violations corresponded to those patients who did not complete the 12-day treatment duration. A descriptive analysis of the baseline variables will be made for each treatment group, followed by a comparison between both groups.

In the secondary analysis a logistic regression model will be built to estimate the effect of dexamethasone and placebo on the patient's functional status measured with the GOSE at one month and at 6 months. The scale will be dichotomized in unfavorable outcome (GOSE 1-6) and favorable outcome (GOSE 7-8). In this analysis the primary outcome will be adjusted by age, pupil reactivity, blood pressure and GCS. To choose a model, the adequacy and goodness of fit will be measured.

Since the severity of the initial injury will significantly determine the final outcome of the patient, regardless of any treatment, the results of this study will be analyzed using the 'sliding dichotomy'. According to this analysis, patients with a less severe initial injury should have a better recovery than those with a severe initial injury. For example, a moderate disability in a patient for whom no more than death or severe disability could be expected is considered a good outcome, and vice versa, consider a moderate disability in a patient with excellent initial prognosis as poor outcome. Patients with a

severe initial injury (GCS score of 4 to 5 or, or with a GCS motor score of 2 to 3) will be considered to have a favorable outcome if the 6-month GOS-E score is 3 or higher. Patients with a moderate-to-severe initial injury (GCS score of 6 to 8 or, GCS motor score of 4 to 5) will be considered to have a favorable outcome if the 6-month GOS-E score is 5 or higher, and those with a less initial injury (GCS score of 9 to 12, GCS motor score of 6) will be considered to have a favorable outcome if the 6-month GOS-E score is 7 or higher.

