FIGURE 1. TRIAL OVERVIEW

[figure not shown]
[figure not shown]

FIGURE 2. MEASURES OF OUTCOME DURING THE TRIAL

Inclusion CT: CT performed in the previous 24 hours before randomisation

End of treatment CT: CT performed in the following 48 hours after treatment period

GOSE: Glasgow Outcome Scale Extended

RPQ: Rivermead post-concussion symptoms questionnaire

TIL: Therapy Intensity Level

NT: Neuropsychological tests: QLIBRI, MOCA, RAVL-T, Coding WAIS IV, CPT, STROOP, TOLDX, Digit span WAIS IV

SUPPLEMENTAL DATA 1.

Primary Outcome measurement

The primary outcome is the Glasgow Scale Outcome Extended (GOSE) performed one month and 6 months after trauma. This scale will be dichotomized in favorable outcome (GOSE 7-8 points) and unfavorable recovery (GOSE≤6 points)

Secondary Outcome measurements

-Compare the number of episodes of neurological deterioration in both groups of patients during the 12 days of treatment.

The number of episodes of neurological impairment will be detected by the Glasgow coma scale and the abbreviated NIHSS scale, during the 12 days of treatment.

An episode of neurological impairment is defined as a worsening of at least 2 points on the Glasgow coma scale or the NIHSS scale, which lasts at least 2 hours, and which cannot be fully attributed to other causes other than that cerebral edema. In order to rule out other causes of neurological deterioration, complementary tests will be performed according to the protocol of action of each hospital. Among these tests are an arterial blood gas analysis, blood test with blood count and biochemistry, electroencephalogram and a cranial CT scan.

Baseline scores to compare subsequent neurological examinations will be performed 30 minutes before starting the study medication. Subsequently, the reference scores will depend on the patient's clinical evolution. After sustained episodes of improvement or worsening in the patient's clinical situation, the baseline scores will be recalculated to reflect the best score of the Glasgow coma scale and the NIHSS before a possible episode of neurological impairment. In those patients in whom it is not possible to perform neurological examinations, the reason will be collected in the Investigator's Study File.

The neurological exams will be performed 3 times per day during the 12 days of treatment.

-Compare the symptoms associated with TBI in both groups of patients during the 12 days of treatment.

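### The sample-size section makes GOSE 7-8 at one month the primary endpoint, the outcome definitions give one and six months, and no rule reconciles them

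*Combined protocol and SAP*

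**What the plan says.** All of the following is current text in the combined protocol and SAP.

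- **Primary outcome:** "The primary outcome is the functional status (outcome) of TBI patients one and six months after the trauma", by GOSE. No cut-off is given here.
- **Supplemental data 1, Primary Outcome measurement:** "The primary outcome is the Glasgow Scale Outcome Extended (GOSE) performed one month and 6 months after trauma". The split into GOSE 7-8 against 6 or lower follows.
- **Sample size and treatment effect size:** "The primary endpoint for the DEXCON TBI trial is the good recovery (GOSE 7-8) one month after the TBI". The next paragraph gives 600 patients, about 80% power, two-sided 5%, 50% against 62%, with 10% inflation included.
- **Estimated event rate:** the 50% control rate comes from the team's previous studies, with no month attached.
- **Secondary outcomes:** deterioration episodes, symptoms, edema volume, adverse events and neuropsychological tests. Six-month GOSE is not on the list.
- **Analysis:** "The primary analysis will compare all patients allocated to dexamethasone versus those allocated to placebo", on a modified intention-to-treat basis, with no month, cut-off or test. A logistic model, labelled secondary, covers "functional status measured with the GOSE at one month and at 6 months", and of that model the plan says "In this analysis the primary outcome will be adjusted by age, pupil reactivity, blood pressure and GCS". A sliding dichotomy, defined on six-month GOSE only, is added without a rank.
- **Interim analysis:** futility is declared if conditional power is below 0.15. The section speaks of a primary outcome variable in the singular but does not say which one.

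**The concern.** A 5% error rate and about 80% power describe one test. The sample-size section has one. The two outcome definitions can be read as giving two, and the plan does not say what happens if they disagree. If dexamethasone is significant at one month but not at six, the sample-size section supports calling the trial positive, while the outcome definitions leave it open. If it is significant at six months only, the reverse applies. The choice could then be made after the results are known.

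The futility rule inherits the problem, because conditional power must be computed for a named endpoint. Depending on when the interim is run, the two months could supply quite different amounts of data.

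**Working it through.** **1. Reproduce the plan's figure.** Inputs from the sample-size section: p1 = 0.50, p2 = 0.62, difference 0.12, two-sided 5% (z = 1.960), 80% power (z = 0.842), 10% inflation. Allocation is 1:1, from the AB/BA blocks under Randomization.

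Pooled two-proportion formula, with mean proportion 0.56:

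n per arm = [1.960 × √(2 × 0.56 × 0.44) + 0.842 × √(0.50 × 0.50 + 0.62 × 0.38)]² / 0.12² = 267.4, so 268.

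Total 2 × 268 = 536, and 536 / 0.9 = 596, against 600 stated.

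Power with 600 less 10%, i.e. 270 per arm: Φ[(0.12 × √270 − 1.960 × √0.4928) / √0.4856] = Φ(0.855) = 80.4%.

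So 600 fits one binary comparison at the full two-sided 5%. It does not show which month, because the 50% rate carries no time point. Only one sentence in the sample-size section identifies one month.

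**2. What two primary time points would mean.** The plan states no success rule, and the documents give no correlation between the months and no six-month effect. The following is illustration only: bivariate normal test statistics with assumed correlation ρ and, for joint power, the same 50% against 62% at both times.

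- Either month suffices, each at 5%: false-positive rate = 1 − P(|Z1| < 1.96, |Z2| < 1.96).
- Both months required: joint power = P(Z1 > 1.96, Z2 > 1.96), with 80.4% for each test at 270 per arm. The false-positive rate stays at or below 5%.

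| Assumed ρ | Either: false-positive rate | Both: joint power |
|---|---|---|
| 0.5 | 9.1% | 69.2% |
| 0.7 | 8.3% | 71.8% |
| 0.8 | 7.8% | 73.4% |

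If alpha were split at 2.5% each (Bonferroni), power per test at 270 per arm would be 71.6%. For 80% per test, 324 per arm are needed: 648 in total, and 648 / 0.9 = 720 after inflation.

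**3. Data available at the interim.** The Interim analysis section sets it at the end of year one with about 100 recruited. Assume even recruitment over 12 months and no wait for follow-up.

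- Reached one month: 100 × 11/12 = 91.7, about 92; 91.7 / 600 = 15%.
- Reached six months: 100 × 6/12 = 50; 50 / 600 = 8%.

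Taking the 10% loss off both parts of each fraction leaves it unchanged (82.5 / 540 and 45 / 540). With the minimum of 60 given under Settings: 60 × 11/12 = 55 and 60 × 6/12 = 30.

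**The case against.** The best case against is that the passages can be reconciled. The sample-size sentence is complete: it gives measure, cut-off and month. The other two places may only describe the instrument and its assessment schedule. That reading is possible but not decisive. Both places say that the primary outcome is GOSE at the two times, under headings that call it primary; the secondary list does not take up six-month GOSE; and nothing says that the sample-size section prevails. Even on this reading, the rank of six-month GOSE stays undefined.

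The adjusted model is weak evidence for two primaries, because the plan labels it secondary. That is correct. It shows only that the term primary outcome is applied to both months.

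The futility endpoint is less open than it might look. The sample-size section mentions the futility analysis immediately before naming the one-month endpoint, which suggests one month. The Interim analysis section does not say so. The data gap also closes if the interim waits for follow-up, and the steering committee section does refer to a review once outcome data are available for the first-year participants.

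A reader might go further and infer that the trial will run at a false-positive rate of 8% to 9%, or that 600 patients are too few. The documents support neither. They adopt no either-or rule and no both-required rule, the correlations are assumed, and 600 is adequate for the single endpoint that the sample-size section names.

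**Conclusion.** The point stands and should be corrected before any comparison of the arms is seen. It is a contradiction between definitions in the current text, not an arithmetic error. The single-endpoint figures are sound (596 recomputed against 600, and 80.4% power), and they cover one month or the other, not both.

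The consequence that needs no assumption is that a result significant at only one of the two months has no pre-specified interpretation. The sizes attached to two primaries (9.1% to 7.8% false positives under either, 69% to 73% joint power under both) depend on assumed correlations of 0.5 to 0.8, and the joint power also on an equal 12-point effect. They show why the rule matters, not what the trial will do. The interim contrast, 15% against 8% of 600, depends on even recruitment and no wait for follow-up.

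**What to change.** - In Primary outcome, Analysis and Supplemental data 1, state that the single primary endpoint is GOSE 7-8 at one month, tested at two-sided 5%, as the sample-size section already says.
- In Interim analysis, state that conditional power is computed for this endpoint.
- In Estimated event rate, state which month the 50% control rate refers to.
- List six-month GOSE 7-8 and the six-month sliding dichotomy as secondary.

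If the team prefers to keep both months as primary, it must state whether either or both must be significant, and restate alpha, power or sample size to match.

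**Cost.** These are wording edits. Under Protocol development they need the steering committee's agreement. Since ethics and AEMPS approval are in place and recruitment is active (Trial status), an amendment to those approvals may also be needed. The one-month option adds no patients and no visits, but six-month GOSE can then no longer be claimed as a primary result. Keeping both months may not be free: the Bonferroni version above needs about 720 patients instead of 600.

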Among the drugs that have been tested in clinical trials in patients with TBI are corticosteroids. Based on the results of the MRC CRASH study (9), the current Clinical Practice Guidelines (10) do not recommend the administration of high doses of methylprednisolone to improve the prognosis for patients with TBI. However, due to the experience of dexamethasone in patients with brain tumors, this glucocorticoid is still used in neurosurgical patients with various pathologies and its role is currently being reassessed in patients with TBI and chronic subdural hematomas (11,12).

In daily clinical practice, patients with TBI and cerebral contusions developing an area of pericontusional edema are among the patients who are occasionally given dexamethasone on the belief that this edema is similar to that of tumors. Clinically, the beneficial effect of dexamethasone in patients with tumors and peritumoral edema, which is primarily vasogenic, has been well demonstrated (13).

Cerebral edema is classified as cytotoxic and vasogenic. Cytotoxic edema is primarily intracellular and appears after ischemic insults. In vasogenic edema, however, water has an extracellular location and appears when there is a disruption or an abnormal increase in the permeability of the blood brain barrier (14). Published studies have described the presence of a mixed component (vasogenic and cytotoxic) in patients with TBI and cerebral contusions (15,16). Experimental studies have shown that the alteration of the blood brain barrier is biphasic. There is a rapid initial opening phase after the trauma that occurs in the first hours. Subsequently, a second opening phase of the blood brain barrier occurs, which usually begins between 3-7 days after the trauma (17). At the clinical level it has been proven that can take days or weeks for the blood brain barrier to return back to normal (17,18). For this reason it is possible that there is a therapeutic window for corticosteroids in this type of patients. However, it is well known that corticosteroids have a beneficial effect on vasogenic edema (as in patients with tumors) but none on cytotoxic edema.

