Dexamethasone doses are those commonly used in neurooncology and there is an extensive experience in its use. It will be a short and descending course: 4mg/6 hours (2 days); 4 mg/8 hours (2 days); 2 mg/6 hours (2 days); 2 mg/8 hours (2 days); 1 mg/8 hours (2 days); 1 mg/12 hours (2 days).

Drug manufacture, blinding and supply of trial treatment

Dexamethasone (Forteocortin®) will be acquired from ERN, SA. Laboratories (Barcelona, Spain). The Son Espases Pharmacy Department will be in charge of developing and conditioning the 4mg, 2mg and 1mg dexamethasone / placebo capsules needed for 12 days of treatment, keeping the researchers blind.

The preparation and conditioning of the capsules will be carried out following the standardized work procedures of the pharmaceutical laboratory and its quality controls, previously authorized by the Agencia Española del Medicamento (AEMPS).

The Son Espases Pharmacy Department will be responsible for identifying the containers and sending them by courier to the participating hospitals. A record of the dispensing of test samples will be kept and will be sent in acknowledgment of receipt for control.

Patients, clinical staff, evaluators of the results as well as the statistical team that will perform the analysis will not know the assigned treatment. A randomization list will be created for each hospital. The randomization sequence will only be known by the Pharmacy Department of Son Espases Hospital.

Administration of trial treatment

Each patient will receive 3 containers with the correspondingly identified doses, and an information sheet explaining dose and frequency for proper oral administration.

Other treatments for traumatic brain injury

There is a wide spectrum of treatments for TBI. As the trial will be conducted in Spain, each participating site should follow its own clinical guidelines for the treatment of TBI patients. There is no need to withhold any clinically indicated treatment in this trial.

Dexamethasone or placebo would be provided as an additional treatment to the usual management of TBI.

Safety and Adverse events

Dexamethasone has a well documented safety profile. Nevertheless, data on adverse events, such as infectious complications, hyperglycemia, gastro intestinal bleeding or appearance of psychotic symptoms will be collected as secondary outcomes and will be presented to the independent Data Monitoring Committee (DMC) for blinded review.

Definitions

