This procedure will be performed again centrally in the 12 de Octubre hospital, Madrid. Previously, the patient's data will be anonymized and the images will be sent through a web platform with a secure server for review. In a central way, the total volume of the contusion will be established as well as the volume of the edema by means of a semi-automatic method using the Analyze software (vesion 10.0; Analyze Direct, Stilwell, Kansas, USA) of which a license is available. The method consists of a semi-automatic analysis in which in each axial section a central voxel is selected and thanks to the density selection, voxels with similar density characteristics are selected.

The performance of measurements in each hospital and subsequent centralization of the images will allow to establish the interobserver and intermethod reproducibility of the measurement of the edema associated with the contusions, in addition to estimating in two ways the difference of measurements at two time points throughout the study and after an intervention.

-Compare the presence of adverse events between the two groups during the 12 days of treatment.

Those adverse effects that have special interest and serious adverse effects will be collected. Side effects of special interest are:

-Metabolic: Hyperglycemia will be especially monitored. The maximum value of capillary glycemia will be recorded daily. The amount of daily insulin that the patient needs to control de glucose level will also be collected.

-Psychiatric: presence of psychotic symptoms using the Confusion Assessment Method (CAM).

-Digestive: Episodes of gastro intestinal hemorrhage; Episodes of epigastric pain, vomiting or reflux symptoms.

-Infectious: Presence of new infectious episodes. Infectious episode will be confirmed in accordance with the Centers for Disease Control (CDC) criteria and mainly based on microbiological criteria.

- Compare the results of the neuropsychological tests between the two groups of patients one month and 6 months after the TBI.

Two neuropsychological evaluations will be performed: 1 month and 6 months after the TBI. Both evaluations will be performed by clinical neuropsychologists, and the protocol to be used will always follow the same procedure and tests. The tests that integrate this protocol are described below:

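### Adverse events are compared between arms only up to the last dosing day, so non-fatal infections and gastrointestinal bleeds after day 12 have no stated comparison

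*Combined protocol and SAP*

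**What the plan says.** Secondary outcomes (Supplemental data) includes "Presence of adverse events between the two groups during the 12 days of treatment" and "Number of episodes of neurological deterioration in both groups of patients during the 12 days of treatment". Supplemental data 1 repeats the first in nearly the same words, "Compare the presence of adverse events between the two groups during the 12 days of treatment", and adds "Those adverse effects that have special interest and serious adverse effects will be collected". The events of special interest are hyperglycemia, psychotic symptoms, digestive events including gastrointestinal hemorrhage, and new infections. Infections are confirmed by CDC criteria, mainly microbiological.

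For deterioration, "The neurological exams will be performed 3 times per day during the 12 days of treatment". No examination schedule after that is described.

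Dose selection gives six two-day steps. Follow-up has the treatment-period form completed when the 12 days end, or at death or discharge if sooner. End of trial for participants keeps each patient in the trial until death or six months. GOSE and neuropsychological tests are done at one and six months. The Figure 2 legend adds "End of treatment CT: CT performed in the following 48 hours after treatment period".

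**The concern.** The window for comparing harm is the same length as the dosing course, with no days added after the last dose. Two of the named harms, infection and gastrointestinal bleeding, can follow from exposure during treatment yet appear, or be confirmed, after it ends. An infection that first shows on day 10 has two days for microbiological confirmation before the window closes, and the text does not say whether one confirmed later counts. If such events are more frequent on dexamethasone, the stated comparison would not include them.

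Clinical deterioration after the drug stops is in the same position. The Background gives a reason to be interested in that period: it says it "can take days or weeks for the blood brain barrier to return back to normal" in these patients.

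At stake is the cause-specific safety profile that will be set beside any benefit on GOSE. The primary comparison is not affected.

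**Working it through.** **1. Length of dosing against length of the window.** From Dose selection, the daily totals in the six steps are 16, 12, 8, 6, 3 and 2 mg, each for two days.

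- Duration: 6 × 2 = 12 days, which agrees with the plan's stated 12 days.
- Total: 32 + 24 + 16 + 12 + 6 + 4 = 94 mg.
- Days after dosing inside the comparison: 12 − 12 = 0.

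**2. Time left uncovered.** Let T be the visit day counted from injury (one month taken as 30 days, six months as 183) and L the days from injury to first dose. The documents do not give L, so 0 to 7 is assumed. Uncovered days = T − L − 12; covered share = 12 / (T − L).

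| L (assumed) | Uncovered to 1 month | Covered share | Uncovered to 6 months | Covered share |
|---|---|---|---|---|
| 0 | 30 − 0 − 12 = 18 | 12/30 = 40% | 183 − 0 − 12 = 171 | 7% |
| 3 | 30 − 3 − 12 = 15 | 12/27 = 44% | 183 − 3 − 12 = 168 | 7% |
| 7 | 30 − 7 − 12 = 11 | 12/23 = 52% | 183 − 7 − 12 = 164 | 7% |

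**3. What reaches beyond day 12.**

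| Item | Latest time | Compared between arms? |
|---|---|---|
| Events of special interest, serious adverse effects | Day 12 | Yes, to day 12 only |
| Neurological deterioration | Day 12 | Yes, to day 12 only |
| Edema volume on CT | Up to 48 h after treatment | Yes |
| GOSE, neuropsychological tests | 1 and 6 months | Yes |
| SAE reports within 24 h | No end date stated | No comparison of later events stated |

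SAE reporting does not fully close the gap. Reporting of adverse events for this trial restricts reports to events reasonably attributable to the drug and leaves out expected complications of TBI, so a late infection might not be reported.

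**4. Illustration of the effect on detecting harm (all event rates assumed).** The plan's 600 patients less 10% give 600 × 0.9 / 2 = 270 per arm. Let p be the control risk over full follow-up, 2p the dexamethasone risk, and s the share of events inside the window, equal in both arms. The observed difference is s·p instead of p. Power is Φ[(d − 1.96·SE0)/SE1], with d the observed difference, SE0 from the pooled variance and SE1 from the separate variances.

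For p = 8%, s = 1: d = 0.08, SE0 = √(2 × 0.12 × 0.88/270) = 0.0280, SE1 = √((0.08 × 0.92 + 0.16 × 0.84)/270) = 0.0278, and power = 0.82.

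| p | s = 1 | s = 0.75 | s = 0.50 |
|---|---|---|---|
| 4% | 0.50 | 0.39 | 0.28 |
| 8% | 0.82 | 0.68 | 0.50 |
| 12% | 0.95 | 0.87 | 0.68 |

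The documents give no value for p or s, so the table shows direction and scale only.

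**5. Analysis set.** The modified intention-to-treat set in Analysis leaves out patients who do not complete 12 days, and End of trial for participants has the drug stopped when an adverse event occurs. The documents do not say which set serves the safety comparison. If it were this one, patients with on-treatment harm could drop out of it.

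**The case against.** The strongest reply is that a 12-day window for intensive daily assessment is a defensible match to a 12-day course in a pragmatic trial, and that later harm is not invisible. Several parts of that stand.

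- **Follow-up continues.** A reader might infer that no patient is followed for harm after the last dose. The adverse event definition covers the whole course of the trial, SAE reporting has no day-12 limit, and participation runs to six months. The gap is in the stated comparison; collection is not shown to stop.
- **Direction of bias.** A reader might infer that the comparison favours dexamethasone. Death or disability from a late infection or bleed enters GOSE at one and six months. Worsening of edema after withdrawal is not described anywhere in the documents; the Background statement on barrier recovery is offered as the reason for a therapeutic window. The course also tapers, and the CT up to 48 hours after treatment could show a very early return of edema.
- **First-year safety review.** A reader might infer that it uses truncated data. Safety and Adverse events does say that adverse events collected as secondary outcomes go to the DMC. But Interim analysis refers to adverse effects collected during the first year, and the DMC section to accumulating data, neither with a 12-day limit.
- **Exposure is early.** By day 8, 84 of 94 mg (89%) has been given, so most exposure has at least four days of observation inside the window.
- **Figure 2 is not shown.** A later safety assessment drawn there cannot be ruled out, though no text describes one.
- **Deterioration cannot simply be extended.** It requires a worsening of at least 2 points lasting at least 2 hours, against a recalculated baseline, with other causes considered. That depends on the thrice-daily examinations.

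What remains is that GOSE does not identify cause, and an infection or bleed that resolves may leave no trace in it.

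**Conclusion.** The point holds in a limited form. The specified arm comparisons of adverse events and neurological deterioration end on the last dosing day, and no readable text defines a cause-specific comparison afterwards. Non-fatal infections and gastrointestinal bleeds that appear or are confirmed after day 12 are the main loss, and an excess of harm may be understated.

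The uncovered time before the one-month visit is about 11 to 18 days, assuming a 30-day month and a start 0 to 7 days after injury. The share of events falling there is unknown, so the size of any understatement cannot be derived from the documents. Nor do they establish a bias in favour of dexamethasone.

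This is an inexpensive improvement to safety reporting. The sample size does not change, because it rests on GOSE.

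**What to change.** Define the arm comparison of serious adverse effects, new infections and gastrointestinal bleeding from first dose to the existing one-month visit, in all randomised patients. Take events after day 12 from hospital records and, for discharged patients, from a standard question at that visit. State that serious adverse events already reported after day 12 enter this comparison.

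Keep the 12-day comparison as a separate on-treatment summary. Leave the protocol-defined deterioration endpoint at 12 days, and list any later clinically recorded deterioration descriptively.

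The cost is protocol wording, a short addition to the form at a visit that already takes place, and retrieval of records. No extra visit or change in treatment is needed. The drawback is that events after discharge rest on records and recall and cannot be confirmed as rigorously as in-hospital events. With blinding maintained, this should affect both arms equally, and the separate 12-day summary keeps the more rigorous data apart.
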